## I. INTRODUCTION

The Blood Safety Continuous Active Surveillance Network (BloodSCAN), is a component of the Sentinel System initiated by the Center for Biologics Evaluation and Research (CBER) as an active surveillance system that focuses on evaluating recipient safety of FDA-regulated blood components and plasma-derived products. The BloodSCAN framework utilizes billing and other electronic health data within the Sentinel System to assess the risk of adverse health outcomes of interest following exposure to blood products among large populations. The ability to assess population risk of blood-product related adverse events complements spontaneous reporting of adverse events to FDA and other existing FDA safety surveillance programs.

In 2016, FDA expanded the data within Sentinel to include inpatient electronic health data from Hospital Corporation of America (HCA). This assessment, which is the first Sentinel utilization of this new inpatient data source, examines the feasibility of utilizing HCA's Sentinel database to capture exposure to blood components and the outcome of transfusion-related acute lung injury (TRALI). The assessment will also describe incidence rates of TRALI subsequent to blood component exposure.

## II. OBJECTIVES

### A. PRIMARY OBJECTIVES

1. To describe identification of potential TRALI cases, risk factors for TRALI, and relevant transfusion exposures in HCA's Sentinel database
2. To describe incidence rates of TRALI subsequent to plasma, platelet, packed red blood cell administration using HCA's Sentinel database
3. To determine through medical chart review the performance of an ICD-9-CM code based algorithm for identifying TRALI
4. To determine through medical chart review the positive predictive value of reported transfused product exposure in identified TRALI cases

### B. EXPLORATORY OBJECTIVES

1. To explore the potential for comparing blood component specific TRALI incidence rates
2. To explore the ability to identify specific categories of blood components, including component type and processing method (e.g., leukocyte-reduced, irradiated)
3. To explore methods for reducing any relevant missing transfusion information in HCA's Sentinel database
4. To describe the distribution of possible patient risk factors, such as age, sex, and relevant comorbidities, among cases of TRALI
5. To describe the distribution of possible transfusion risk factors, such as volume of transfusion and component processing (e.g., leukoreduction, irradiation) among cases of TRALI
6. To identify which HCA data elements are included in the Sentinel Common Data Model (SCDM) that are useful/relevant for studying TRALI, and to identify additional inpatient data elements that may be useful but are not included in the SCDM

### III. BACKGROUND

#### A. PUBLIC HEALTH SIGNIFICANCE AND STUDY MOTIVATION

Although blood transfusions are administered in many hospitals on a daily basis, patient and exposure associated risk factors for many non-infectious adverse events are often poorly understood. Transfusion-related Acute Lung Injury (TRALI) is a rare but serious life threatening adverse event which occurs during or within 6 hours of transfusion. TRALI is characterized by respiratory distress and pulmonary edema, and is a leading cause of reported transfusion-related mortality in the United States. Despite voluntary measures taken by the transfusion community to reduce risk of TRALI, 41% of transfusion-related fatalities reported to the U.S. Food and Drug Administration between years 2010 and 2014 were attributed to TRALI. TRALI is difficult to diagnose, relies on clinician case recognition skills, and commonly accepted case definitions have varied over time, likely resulting in under- or inconsistent recognition. Reporting of TRALI is not universally required in the United States, although blood transfusion services are required to report fatal complications of blood transfusions to the FDA. These challenges leave us with an incomplete understanding of the epidemiology and attributable burden of these serious transfusion-related pulmonary complications. Risk factors in recipients (e.g., smoking status) and in transfused blood products (e.g., antibodies, bioreactive substances, older RBC storage age) have been noted, and only recently have been described in general populations of transfused patients. Availability of large administrative and electronic healthcare databases is providing new opportunities to examine serious but rare transfusion associated adverse events such as TRALI.

Ultimately, development of a surveillance system to monitor adverse events following transfusion of blood and blood products/components could inform FDA regulatory actions and impact physicians' ability to assess and potentially mitigate risks for individual patients.

#### B. HOSPITAL CORPORATION OF AMERICA

Hospital Corporation of America (HCA) is a leading provider of inpatient services, operating in 20 states and the United Kingdom. HCA is comprised of locally managed facilities, and currently includes more than 165 hospitals and 115 freestanding surgery centers. Nearly 5 percent of all inpatient care delivered in the United States is provided by HCA facilities; this currently includes approximately 26 million patient encounters per year. As a large network of acute inpatient hospitals as well as other facilities, HCA provides a unique new set of data to the Sentinel distributed data network.

HCA became a full Sentinel Data Partner in January 2016, and has transformed available data into the Sentinel Common Data Model (SCDM). Status as a full Sentinel data partner signifies that the Sentinel Operations Center (SOC) has approved the HCA's Sentinel database as SCDM-compliant, quality-checked and query-able. The HCA Sentinel database currently includes approximately 2 million inpatient encounters per year, as well as emergency room and outpatient visits to HCA facilities. HCA's data transformation includes two new Sentinel tables (current structure of these tables is included in Appendix A), which capture inpatient pharmacy and inpatient transfusion data.

#### C. INPATIENT RED BLOOD CELL, PLASMA AND PLATELET ADMINISTRATION

More than 90% of blood transfusions in the United States are performed in inpatient settings. The 2013 National Blood Collection and Utilization Survey includes estimates for the amount of blood collected and transfused in the United States per year. This report estimates 13,180,000 whole blood (WB) and red blood cell (RBC) units were transfused in the United States in 2013. Estimates of platelets transfused totaled 2,281,000 units (including 128,000 whole blood derived platelets and 2,137,000 apheresis

platelets). An estimated 3,624,000 units of plasma were also transfused. Thus, in 2013 the most commonly transfused blood component pertaining to this protocol was RBCs, followed by plasma, and platelets. These numbers provide some context in terms of what may be expected in terms of blood components transfused per year in HCA hospitals.

#### D. TRANSFUSION-RELATED ACUTE LUNG INJURY (TRALI)

TRALI is a leading cause of transfusion related fatalities in the United States. Broadly, TRALI is defined as the onset of respiratory distress during or within 6 hours of blood transfusion. TRALI is relatively rare, and the estimated U.S. incidence of TRALI has varied widely across studies. This variation may be partially attributed to the lack of population-based TRALI studies and focus on specific hospitals or centers, but studies in critically ill patients have noted higher TRALI incidence rates. However, a recent population-based study examining TRALI occurrence in elderly Medicare beneficiaries estimated an overall rate of 22.5 per 100,000 transfused inpatient stays. TRALI has been associated with transfusions of RBCs, fresh frozen plasma (FFP), and platelets. It has also been reported rarely after intravenous immunoglobulin treatment.

TRALI is a syndrome for which no specific clinical test is available and diagnosis is based on clinical, laboratory and radiological parameters. The Centers for Disease Control and Prevention National Healthcare Safety Network has defined TRALI as new onset of acute lung injury (ALI) occurring during or within 6 hours of blood transfusion (**Table 1**). The term ‘Possible TRALI’ is used when there is a temporal relationship to an alternative ALI risk factor (**Table 2**). Additionally, the literature suggests that some patients may meet the TRALI definition, but have symptoms beginning outside of the six hour post-transfusion window, and thus a delayed TRALI definition has been suggested to capture such patients.

**Table 1: Transfusion Related Acute Lung Injury (TRALI) definitions**

Definition	Clinical Description
Definitive TRALI 	
 
1. No evidence of acute lung injury (ALI) prior to transfusion AND
 
2. ALI onset during or within 6 hours of transfusion AND
 
3. Hypoxemia defined by any of these methods: 
 
•PaO2 / FiO2 ≤300 mm Hg
 
•Oxygen saturation is < 90% on room air
 
•Other clinical evidence
 
 AND
 
4. Radiographic evidence of bilateral infiltrates AND
 
5. No evidence of left atrial hypertension (i.e. circulatory overload) AND
 
6. No temporal relationship to an alternative risk factor for ALI during or within 6 hours of completion of transfusion
 

Possible TRALI 	Same as above EXCEPT there is a temporal relationship to a specific ALI risk factor (Table 2)
Delayed TRALI definition, defined in critically ill patients	
Delayed TRALI 	Same as for possible TRALI except allows for symptom onset within 6 to 72 hours of blood transfusion

**Table 2: Alternate risk factors for Acute Lung Injury (ALI)**

Direct Lung Injury	Indirect lung injury
Aspiration	Severe sepsis
Pneumonia	Shock
Toxic inhalation	Multiple trauma
Lung contusion	Burn injury
Near drowning	Acute pancreatitis
	Cardiopulmonary bypass
	Drug overdose

TRALI is believed to be caused by immune mediated mechanisms that lead to neutrophil activation, damage to endothelial cells, and pulmonary edema. A two-hit hypothesis has been suggested for TRALI, with the first hit associated with patient risk factors that result in primed neutrophils adhering to the patient’s pulmonary endothelium. The second hit may be antibody-mediated or non-antibody mediated, but relates to blood transfusion mediators activating endothelial cells and pulmonary neutrophils causing capillary leakage and thus pulmonary edema.

According to the two hit model, risk factors for TRALI are both patient and transfusion dependent. Blood products containing plasma have been commonly associated with TRALI, and HLA antibodies in blood products containing plasma from female donors specifically have been implicated. Blood product age (i.e., longer storage) may play a role. Numerous patient risk factors have been implicated, and include sepsis, cardiac surgery, trauma, and other ALI risk factors. Higher incidence of TRALI has also been reported in patients with alcohol use disorder, patients who smoke cigarettes, and in patients with end stage liver disease. ICU patients have also been reported to have a higher incidence of TRALI, presumably due to underlying co-morbidities.

## IV. METHODS

### A. STUDY POPULATION AND DATA SOURCES

This assessment will include HCA hospitals systematically contributing inpatient transfusion data to the Sentinel Distributed Database (SDD). The population will consist of all hospitalized individuals with evidence of a transfusion during the period of interest, September 2013 through September 2015. This time period was selected because prior to September 2013 many HCA hospitals were not systematically providing transfusion data.

Within this period, individuals will be included in the analyses if they had evidence of TRALI (defined below) in HCA’s Sentinel database or b) had evidence of a transfusion of a relevant blood component/product (defined below) in HCA data. This project will also attempt to confirm TRALI and transfusion information for TRALI cases through medical chart review. As HCA is a new Sentinel Data Partner, exploratory analyses will focus on feasibility of examining patient and transfusion risk factors in HCA data, as well as identification of blood components, including component type and processing method (e.g., leukocyte-reduced, irradiated). We will use information derived from medical chart review to inform these explorations.

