## B. STUDY DESIGN AND OVERVIEW OF ANALYSIS PLAN

A retrospective cohort study design is proposed to examine TRALI occurrence among HCA patients transfused in a hospital inpatient setting between September 2013 and September 2015. Within this cohort, capture of potential TRALI cases, risk factors for TRALI, and relevant transfusion exposures in HCA’s Sentinel database will be described, and incidence rates of TRALI subsequent to plasma, platelet, packed red blood cell administration using HCA’s Sentinel database will be calculated. Medical chart reviews will be conducted to confirm the outcome (TRALI) and the transfusion exposure, and the positive predictive values of each electronic algorithm will be evaluated. The gold standard will be medical chart confirmed outcomes and transfusion exposures.

Unadjusted TRALI rates (per 100,000 inpatient transfusion stays) will be calculated overall, by year, blood component groups, sex, age, race, and number of units transfused. If appropriate transfused unit data are available, unadjusted TRALI rates per number of units transfused will also be calculated. Medical charts will be utilized to confirm the TRALI outcome and transfusion exposure in identified TRALI cases, and the positive predictive value of an ICD-9-CM based algorithm for identifying TRALI will be presented. Similarly, the positive predictive value of reported transfused product exposure and medical chart confirmed exposure in identified TRALI cases will be presented.

As HCA is a new Sentinel Data Partner, exploratory analyses are included as feasibility analyses (see page 2). The workgroup will explore the potential to compare blood component specific TRALI rates, examine TRALI patient and transfusion risk factors, and ability to identify specific categories of blood components, including component type and processing method (e.g., leukocyte-reduced, irradiated). Finally, the workgroup will describe which HCA data elements are included in the SCDM that are useful/relevant for studying TRALI, and which inpatient data elements could be useful but have not been included, and to assess the feasibility and need for adding these elements based on their availability, accuracy, and usefulness for blood and other biological products.

The plan is shown schematically below:

Relative Timing	Method	Analysis	Data to use

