#### D. OUTCOME DEFINITION

Potential cases of TRALI will be identified with the codes included in **Table 4**. As TRALI is likely under-diagnosed, this protocol focuses not only on the TRALI specific ICD-9-CM code (ICD-9 518.7), but also on specific respiratory failure codes described above in combination with an ICD-9-CM code for a transfusion reaction. **Table 5** includes the electronic criteria to identify potential cases of TRALI in the HCA Sentinel database. These criteria include ICD-9-CM codes, as the time-period of interest for this protocol precedes the transition to ICD-10-CM coding in the United States.

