## 2. Calculation of Incidence Rates

Unadjusted incidence rates of TRALI occurrence after any transfusion will be calculated, along with 95% confidence intervals. Any transfusion will be defined as exposure to plasma, platelets (PLT), or packed red blood cells (RBC) as defined in HCA's Sentinel database. TRALI will be defined using ICD-9-CM based codes in HCA's Sentinel database, and the primary analysis will focus on TRALI as defined by criterion A (Table 5). Unadjusted TRALI rates (per 100,000 inpatient transfusion stays) will be stratified by year, blood component groups (i.e., plasma, PLT, and RBC), age, sex, race, and quantified units. If data on the number and type of component unit(s) transfused are available, unadjusted TRALI rates per number of units transfused will also be calculated. If feasible, quantified units will be examined separately for children and adults.

In addition to identifying rates of TRALI occurrence after any exposure to plasma, PLT, or RBC during an inpatient stay, if adequate sample size is available we will also explore exposure to RBC-only, plasma-only, and PLT-only. Exposure to multiple blood component types (i.e., plasma and PLT, RBC and PLT, plasma and RBC, plasma and RBC and PLT) or non-specific blood components (if relevant) will also be described.

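### The cohort closes on transfusion date, so the stated reason for using ICD-9-CM codes alone does not cover stays still open at the end of September 2015; the likely bias is small and downward

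*Protocol*

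**What the plan says.** Protocol IV.A defines the population as "all hospitalized individuals with evidence of a transfusion during the period of interest, September 2013 through September 2015". IV.B repeats the same anchor: "HCA patients transfused in a hospital inpatient setting between September 2013 and September 2015". Neither section gives an admission or discharge limit, and the inpatient encounter type in Table 7 (Appendix A) adds none.

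The reason given for the window concerns its start only: "This time period was selected because prior to September 2013 many HCA hospitals were not systematically providing transfusion data". A further sentence in IV.A reads "Within this period, individuals will be included in the analyses if they had evidence of TRALI (defined below) in HCA’s Sentinel database", with transfusion as the alternative route in. It gives no rule for a stay that straddles the end of the period.

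Potential cases are found with the ICD-9-CM codes in Tables 4 and 5. IV.D explains the restriction to that system: "the time-period of interest for this protocol precedes the transition to ICD-10-CM coding in the United States". In IV.F.2 the primary numerator is Criterion A (code 518.7), and "Unadjusted TRALI rates (per 100,000 inpatient transfusion stays) will be stratified by year". IV.D uses the same electronic criteria to select charts for review.

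**The concern.** Entry depends on when the patient was transfused. Detection depends on the codes attached to the whole stay. The sentence in IV.D joins the two by saying that the period comes before the coding change, but that holds only for stays that also end before the change.

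Read literally, the entry rule admits a patient transfused on 29 September 2015 and discharged in October. If that stay is coded in the new system, it cannot carry any code in Table 5. It then counts as a transfused stay without TRALI whatever happened, and its chart is never selected. At stake is a downward bias in the Criterion A rate, concentrated in the last stratum of the by-year table.

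**Working it through.** **The protocol's own figure.** There is no power calculation. The only planning figure is fewer than 200 cases (IV.F.5), given without a derivation, so it can be checked for plausibility but not reproduced. Two inputs come from the protocol: about 2 million inpatient encounters per year (III.B), and 22.5 per 100,000 transfused stays from the cited Medicare study (III.D).

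- Encounters in 25 months: 2,000,000 × 25/12 = 4,166,667.
- Cases = 4,166,667 × transfused share × 22.5/100,000. Assumed shares of 5%, 10% and 20% give 47, 94 and 188 cases.
- The bound of 200 is reached at a share of about 21%, so the figure is plausible.

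**Length of the window.** Read as 1 September 2013 to 30 September 2015, the window has 760 days. January to September 2015 has 273 days.

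**Assumptions not in the protocol.**
1. Code version follows the discharge date.
2. The switch came right after September 2015.
3. The mean time R from first in-window transfusion to discharge is 3 to 14 days.
4. Transfused stays arise at a steady rate.

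**Formula.** With λ qualifying stays per day, about λR are open when the window closes, out of λ × 760 in all. The undetectable share is therefore R/760 overall and R/273 in the 2015 stratum. Nothing leaves the denominator, so the rate falls by the share of cases lost, and the relevant R is the one for cases. The last two columns show what a true rate of 22.5 per 100,000 would read.

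| R (days) | Lost overall | Lost of 200 cases | Lost in 2015 | Rate overall | Rate in 2015 |
|---|---|---|---|---|---|
| 3 | 0.39% | 0.8 | 1.10% | 22.41 | 22.25 |
| 7 | 0.92% | 1.8 | 2.56% | 22.29 | 21.92 |
| 14 | 1.84% | 3.7 | 5.13% | 22.09 | 21.35 |

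As an extreme, R = 20 gives 2.6% overall and 7.3% in 2015.

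**If assumption 1 or 2 fails.** If code version follows the admission date, or the date of a diagnosis made within hours of a September transfusion, the loss is nil or close to it. A switch later than 1 October also shrinks it. Across these possibilities the bias runs from zero to the figures in the table.

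**Sampling error.** Exact Poisson 95% limits, relative to the estimate, are -13% to +15% at 200 cases, -19% to +22% at 100 and -26% to +32% at 50. With 200 cases in all, the 2015 stratum would hold about 200 × 273/760 = 72, so its limits lie between the last two.

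**Comparison of stays with and without TRALI (IV.F.4).** Only missed cases are misplaced. At R = 14 they number 22.5/100,000 × 1.84%, or about 4 per million stays.

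**A tempting remedy.** Keeping the transfusion-date start and adding a discharge limit at the end drops long September stays selectively. Suppose cases have R = 10 and all stays R = 5. The remaining rate ratio is (1 - 10/760)/(1 - 5/760) = 0.9868/0.9934 = 0.993. With R = 14 and R = 8 it is (1 - 14/760)/(1 - 8/760) = 0.9816/0.9895 = 0.992. A bias of about 0.7% to 0.8% remains, roughly half of the 1.3% to 1.8% without any limit.

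**The case against.** The strongest case against raising this has three parts.

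First, both coding premises come from outside the document. IV.D says only that the period precedes the transition. This stands, and it is why the size is given as conditional. It does not rescue the IV.D sentence, which argues from the period while the cohort contains stays that can run beyond it.

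Second, the protocol nowhere says that open stays are kept, and the encounter date that closes the cohort could be set in an analysis plan or in the cohort program. An end rule may indeed exist elsewhere. But IV.A says that all patients transfused in the window are included, and both the entry rule and the reason for the code system are stated here. Followed as written, they do not fit together.

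Third, the effect is well inside sampling error, the analyses are expected to be descriptive (IV.F.5), and no test between years is planned. This stands in full and limits the point to a minor correction.

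A reader might infer more, and the documents do not support it:

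- **A distorted comparison group.** A reader might think the stays without TRALI would look longer-staying and sicker. At a few misplaced cases per million, that cannot happen to any visible degree; all other straddling stays belong in that group. For mechanical ventilation the direction may even reverse, because IV.F.4 identifies it with ICD-9-CM procedure codes: if procedure coding switched too, straddling stays would look unventilated.
- **A damaged validation.** Positive predictive value is conditional on meeting an electronic criterion, so undetected stays do not enter it. At most a few charts go unreviewed.

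**Conclusion.** The point holds as a minor correction. The cohort rule in IV.A and IV.B closes on transfusion date, and the justification in IV.D does not extend to stays still open at the end of September 2015.

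Under the two coding assumptions, the Criterion A rate is biased downward by 0.4% to 1.8% overall and 1.1% to 5.1% in the 2015 stratum. At the upper end that is about 4 cases in 200. The size rests on an assumed mean of 3 to 14 days from transfusion to discharge; if cases stay longer than other transfused patients, the upper part of the range is the relevant one. The bias has a known direction and is cheap to remove, which is the reason to act on it. It does not undermine the primary rate or the validation objectives.

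**What to change.** In IV.A and IV.B, define eligible stays by the same encounter date at both ends: discharge from September 2013 through 30 September 2015, with a qualifying transfusion in the stay and all diagnoses coded in ICD-9-CM. Long stays lost at the end are then matched by long stays that began before the window and were discharged inside it.

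That balance needs adequate transfusion capture for stays begun before September 2013, which IV.A gives reason to doubt. If capture is inadequate, keep the transfusion-date start and close transfusion entry about a month earlier, for example on 31 August 2015. Only stays lasting more than a month after the transfusion could then straddle the switch.

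Apply the chosen rule to numerator, denominator and chart selection alike. Report the number of straddling stays excluded, and reword the IV.D sentence so that it refers to the included stays and not to the period.

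**Cost.** The change takes protocol text and one line in the cohort program. The discharge-date rule loses about 1% of stays (7/760 = 0.9% at R = 7), none of which could yield a detected case under the assumptions above. The earlier close loses about 4% (30/760 = 3.9%), including some September cases that could have been detected.
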